1.1 SYNOPSIS

Grant Title	Patient-centered Team-based Primary Care to Treat Opioid Use Disorder, Depression,				
	and Other Conditions				
Intervention and Patient Facing Title	More Individualized Care: Assessment and Recovery through Engagement (MI-CARE)				
Précis	The MI-CARE trial is a randomized encouragement trial that will test whether offering a primary care-based collaborative care (CC) model can increase opioid use disorder (OUD) treatment and improve depression outcomes among patients with: a) recent electronic health record (EHR) documentation of depressive symptoms, and b) evidence of OUD documented in the prior year. The trial will automatically identify a total of 800-1,000 primary care patients across two health systems: Kaiser Permanente Washington and Indiana University Health. Half of patients automatically identified as eligible for the trial will be randomly selected to be offered the MI-CARE intervention. A pilot study was conducted prior to fielding the trial to finalize workflows in the two participating health systems, and refine recruitment, engagement and materials but could not assess engagement rates as about half of eligible patients were "hand-picked" for outreach to optimize diversity and inform refinement of the intervention.				
Objective	The study objective is to evaluate the effectiveness of offering eligible primary care patients the MI-CARE CC program when compared to usual primary care. Among all eligible primary care patients, MI-CARE and usual primary care will be compared to assess the following outcomes: • Aim 1: Days of OUD medication treatment (buprenorphine) • Aim 2: Improvement of depression symptoms. • Aim 3 (intervention arm only): Examining a) implementation using mixedmethods formative evaluation including reach, adoption, and implementation fidelity, and b) nurse care manager time needed to support the MICARE intervention.				
Target Population	Using EHR and claims data we will identify and enroll 800-1,000 English-speaking primary care patients, 18 years and older, with a Patient Health Questionnaire (PHQ) depression score of 10 or higher in the prior week and an indication of OUD in the prior year.				
Research Sites	 Kaiser Permanente Washington (KPWA) (enrollment site) Indiana University Health (IUH) (enrollment site) Kaiser Permanente Northwest (KPNW) (formative analysis, nurse support and training) 				
Non-Research Sites	University of Washington (nurse support and training)				

	 University of New Mexico (nurse support and training) Boston Medical Center (nurse support and training) Montana State University (nurse support and training) Purdue University (pharmacoepidemiology consultation) 				
Trial Randomization	1:1 (offered intervention: usual care), stratified by site				
Study Intervention	The MI-CARE CC intervention is offered by a nurse care manager (NCM) and delivered by telephone (or video) visits to consenting patients. The CC intervention addresses OUD, depression, and other common co-occurring conditions (e.g., pain, sleep, anxiety, suicidality, prescribed opioids or benzodiazepines, other substance use etc.). CC consists of 5 components: • Population-based Care: All eligible patients are managed proactively with outreach and a study patient registry so that patients don't "fall through the cracks" of primary care. • Patient-centered Team Care: The NCM and a primary care team work together to provide patient-centered care. • Evidence-based Care: The NCM supports evidence-based psychosocial and pharmacologic treatments. • Measurement-based Treatment to Target: The NCM uses systematically collected patient reported outcomes to support engagement and treatment adjustments. • Accountable Care. The NCM, the expert consultants at each site, and primary care team are responsible for individual patients and the population of patients.				
Usual Care Comparator	Participants in the eligible target population who are not randomized to be offered the MI-CARE CC intervention. Usual care participants have no contact with the study.				
Participant Duration	12 months from the date of randomization with 1 additional month allowed for patients to complete any annual PHQ from the health system (13 months, overall).				
Outcomes	All outcomes are obtained exclusively from secondary data sources. The trial will test whether patients randomized to be offered the MI-CARE CC intervention, compared to those randomized to usual care: (1) have a significantly greater number of days of medication treatment for OUD over the 12-month follow-up (primary outcome); (2) have a greater reduction in depression symptoms on the PHQ over 12-month follow-up (powered secondary outcome); To support future implementation, the trial will also examine measures of: (3) reach of the intervention, adoption of OUD treatment by primary care providers, and implementation fidelity of the intervention, as well as nurse care manager effort required per patient in CC intervention (CMS billable and nonbillable hours). Secondary outcomes include composite outcomes to assess: (1) Treatment with buprenorphine or clinical response of depressive symptoms;				

	(2) Adverse events relating to depression or opioid use (e.g., suicide attempt, overdose, hospitalization, or death); and(3) Serious opioid-related events.
Study Duration	31 months (main trial launch through end of data collection from all sources)

1.2 SCHEMA FOR CLINICAL TRIAL

1.3 SCHEDULE OF ACTIVITIES

ACTIVITY OR EVENT	DESCRIPTION	SCHEDULE				
Identify eligible patients from EHR/claims and randomly select 50% to be offered CC (MI-CARE arm)	Eligible adult patients (PHQ score ≥ 10 in the 7 days prior to a given week's data extraction date; OUD diagnosis in prior year) are enrolled in the trial automatically; 50% of the eligible cohort will be randomly selected to be offered the MI-CARE intervention. The "index date" is the randomization date.	Day 0 = Date of randomization				
MI-CARE CC ARM ONLY						
PCP and introductory patient recruitment outreach	NCM has initial contact with PCP via standard modes of clinical communication at KPWA and IUH. Patient initial outreach could be by mail, patient web portal, or pre-verified email (IUH only). Initial outreach is followed by phone outreach attempts.	Day 1 (PCP) / up to 4 (patient) – various (may delay patient outreach based on clinical scenario)				
Consent patients for MI- CARE program	NCM administers verbal consent by phone. An information sheet is provided after the call.	Day 2 – various				
Intervention delivery	Collaborative care program delivered by NCM to consenting participants.	(As earlier as) Day 3 – Day 365				
BOTH MI-CARE AND USUA	BOTH MI-CARE AND USUAL CARE ARMS					
Participation dates	 Secondary data collection for primary outcome analyses. 	Day 0 – Day 365				
PHQ participation dates	 Data collection for Aim 2 outcomes involving PHQ data begins day 30 and ends 395 days after randomization. An additional 30 days is allowed for the health system to capture PHQ screening collected on an annual basis. 	Day 30 – Day 395				

2 INTRODUCTION

2.1 RATIONALE FOR TREATING OUD, DEPRESSION AND OTHER CONDITIONS IN PRIMARY CARE

The United States is in the midst of an opioid epidemic and evidence-based treatment for opioid use disorders (OUD) requires medications.^{2,3} While methadone is the oldest treatment for OUD, it can only be provided in specially accredited outpatient treatment programs. Two effective medication treatments for OUD - buprenorphine⁴ and injectable naltrexone - can be provided in primary care.^{5, 6}

2.1.1 NEED FOR IMPROVED ACCESS TO OUD TREATMENT

Experts recommend that most OUD can be treated with buprenorphine and injectable naltrexone in primary care for several reasons.² First, access to methadone maintenance in external outpatient treatment programs is severely limited. Moreover, many specialty "rehab" treatment programs do not offer medications (often due to unfounded beliefs that all medication treatment of addiction is wrong or lack of prescribers on staff). There are also not enough prescribing addictions specialists to treat all patients with OUD, and stigma prevents most people from seeking specialty treatment for OUD.⁷ Finally, medication treatment in primary care alone is effective for OUD: adding specialty addictions-focused counseling to medication treatment for OUD has not been shown to improve outcomes.⁸ Thus, providing treatment integrated with primary care is logical. It may lower barriers to access, and primary care providers (PCPs) can also treat common co-occurring disorders like depression, pain, and insomnia.

2.1.2 NEED TO INCREASE ACCESS TO TREATMENT OF OUD IN PRIMARY CARE

OUD treatment is not yet accessible in most primary care settings. About 80% of people with OUD seen in primary care are not being treated for OUD.^{9, 10} PCPs can be concerned about taking on the complexity of treating OUD without systems to support high quality care. In this way, OUD is akin to anticoagulation or diabetes, or medications for depression: primary care can manage it, but systems are needed to support high quality care.

2.1.3 NON-STIGMATIZED PATIENT ENGAGEMENT IS CRITICAL FOR OUD¹¹

Given the stigma associated with all substance use disorders, including OUD, many patients do not disclose their OUD symptoms. Those who have prescription medication OUD may be worried about losing their opioid supply. While some patients with OUD self-refer to primary care-based OUD treatment, if it is available, many others are diagnosed with OUD but do not receive OUD treatment. Patient-centered engagement is therefore critical to increasing access to OUD treatment. However, it has received relatively little focus by researchers.

No effective approach is known for engaging non-treatment seeking patients with OUD in treatment, and little research has targeted this important issue.

2.1.4 HIGHER MEDICATION DOSE AND LONGER RETENTION IN OUD TREATMENT IS ASSOCIATED WITH REDUCED MORTALITY

Higher methadone and buprenorphine dose has been associated with retention and survival.¹² Further, there is a recognized need to improve retention in OUD treatment, ideally 90 days at a minimum, although many experts consider that lifelong treatment is safest. Generally, retention has not been high, with only 25-50% of patients treated with buprenorphine receiving at least 180-days of OUD medication treatment in observational studies.

2.1.5 DEPRESSION AND OTHER COMMON COMORBID CONDITIONS INTRODUCE ADDITIONAL BARRIERS TO OUD TREATMENT

Effective treatment of OUD is complicated by the high prevalence of comorbid conditions including depression, anxiety, pain, insomnia, and other substance use disorders. ¹³⁻¹⁵ In a sample of primary care patients with OUD, the prevalence of comorbid conditions were: 50% depression, 41% anxiety, 19% insomnia, 82% pain, 31% additional substance use disorders. ¹⁶ More than half of patients on medications to treat OUD report chronic pain ¹⁷ and, when present, pain is associated with increased opioid craving and illicit opioid use, as well as poor adherence to medication to treat OUD. ¹⁸ Many patients with OUD view pain as central to both the onset and maintenance of their OUD symptoms. ¹⁹⁻²¹ Addressing pain and comorbid mental health and substance use may be critical for treatment engagement and efficacy.

2.1.6 COLLABORATIVE CARE IS A PROVEN MODEL FOR IMPROVING DELIVERY OF EMPIRICALLY SUPPORTED BEHAVIORAL HEALTH TREATMENTS TO PRIMARY CARE PATIENTS

Collaborative care enhances engagement and retention in mental health treatment. The collaborative care (CC) model was developed more than thirty years ago to address failures in the delivery of effective depression treatment.²² Rather than a treatment in and of itself, CC is a model in which a care manager supports delivery of effective treatment components based on principles of effective chronic illness care. The CC model includes 5 components: population-based care, patient-centered team-based care, evidence-based care, measurement-based care with treatment to target, and accountability. In practice, CC adds both a care manager proactively engaging patients in care management and a psychiatric consultant to the primary care team in order to provide high quality, evidence-based treatments over time.²² CC has been shown to improve outcomes for depression, other mental health and alcohol use disorders, and pain,^{23, 24} but no study has demonstrated the effectiveness of CC for a substance use disorder and mental health condition simultaneously.

2.1.7 COLLABORATIVE CARE FOR OUD ALONE HAS NOT BEEN SHOWN EFFECTIVE IN A TRIAL

CC has also been used to support primary care for OUD and has been found to increase access to OUD treatment.⁵ Observational studies of the OUD CC model developed and implemented throughout

Massachusetts suggest that its adoption results in increases in the number of patients treated with buprenorphine (~100 patients/nurse) and impressive retention (12-month retention rates of 67% in community settings). However, this program did not actively outreach or engage non-treatment seeking patients (patients self-referred who wanted treatment). No randomized control trial has demonstrated that offering CC for OUD alone increases access to OUD treatment (i.e., encourages patient engagement in such care) and/or improves OUD outcomes. Several efficacy trials of nurse care management in patients with OUD-alone, who consented to be in the trials, have found no benefit for OUD.

2.1.8 COLLABORATIVE CARE FOR OUD COMBINED WITH COMMON COMORBID BEHAVIORAL HEALTH CONDITIONS IS UNTESTED

CC is increasingly being used to address diverse behavioral health conditions, conditions often comorbid with OUD (e.g., depression, anxiety, pain, and alcohol use disorders).²² Further, research has shown that CC can address multiple conditions simultaneously.^{24, 28} However, it is unknown how to optimally integrate CC for OUD with CC for depression, other mental health and substance use disorders, or chronic pain. Moreover, while only ~20% of primary care patients with OUD have EHR-documented OUD treatment, little is known about what proportion would accept OUD treatment if it were offered in primary care. The MI-CARE trial was designed to address that gap and test whether offering CC to patients with OUD and depression would increase OUD treatment in primary care and improve depressive symptoms.

2.2 RATIONALE FOR ENCOURAGMENT TRIAL DESIGN

2.2.1 IMPORTANCE OF TRIALS THAT ASSESS WHETHER OFFERING CC PROACTIVELY TO PRIMARY CARE PATIENTS WITH OUD AND BEHAVIORAL HEALTH CONDITIONS IMPROVES OUTCOMES

Most CC trials for depression and other behavioral health conditions have been efficacy trials that randomized patients after consent. The treatments evaluated in such traditional clinical trials may yield outcomes quite different from outcomes of more typical treatment by real world providers. These trials indicate if CC is effective for those who are interested, but do not assess the population benefit of offering CC. Such trials have important limitations. First, review of published CONSORT diagrams from these studies suggests many had relatively low rates of participation. Thus, while some patients do benefit, many were not interested. However, these low rates of engagement may not be generalizable: there is a difference between being willing to consider care from a CC nurse (e.g., MI-CARE) and being open to participating in a more traditional randomized controlled trial of CC. Evaluating the population benefit is even more important for studying CC for OUD. OUD treatment is more stigmatized than depression. Many patients are not initially interested in medications or other "treatment" for OUD, and many assume that treatment means "going to rehab," so a trial offering "treatment" for OUD runs the risk of attracting a very small group of "treatment ready" individuals. Those willing to participate in a

traditional efficacy trial may also be those most motivated to address their substance use, potentially a much smaller subset of the broader group of patients presenting with these problems in everyday primary care practices.

The question this pragmatic trial seeks to answer is: "If we offer a CC service to patients with evidence of OUD and depression, what is the benefit among people to whom it's offered?" This CC program prioritizes patient-centered, non-stigmatized engagement and assessment of OUD recognition and readiness for OUD treatment, followed by shared decision making. An important element of this design is that the outreach must be more aligned with how patients would be approached, assessed, and engaged in clinical care, and then offered an opportunity to decide if the program interests them. This is a critical, because patients with a history of opioid related problems are often hard to engage and refining a clinical outreach process that is acceptable to patients and enhances engagement is a critical objective of the MI-CARE study.

2.2.2 IMPORTANCE OF AVOIDING ACTIVATION OF CONTROLS THROUGH STUDY RECRUITMENT AND ASSESSMENT

Paradoxical as it may seem, while many patients with OUD and other substance use are ambivalent about seeking and sustaining substance use-related treatment (and, hence, conventional trials likely selectively attract those most motivated for treatment), the softer nudge of outreach and self-assessment characteristic of an "assessment only" usual care study arm has been shown to motivate positive behavior change (reduced substance use) in substance use disorder studies. In the CHOICE trial of CC for alcohol use disorders, ²⁹ patients reported being motivated to change their behavior based on information letters from their PCPs, recruitment outreach, and study assessments (which led them to think about their symptoms and reasons for change). Thus, recruitment could motivate the control arm, biasing the study to the null and missing the true impact of the CC program. In short, control arm patients outreached or administered study assessments are not experiencing true "usual care," and control patients could be activated to change their behavior.

2.2.3 BENEFITS OF ENCOURAGEMENT TRIAL DESIGN

Given the limitations of conventional trial designs described above, this study adopts an encouragement trial design such that all patients in participating healthcare systems who meet clinical eligibility criteria are enrolled in the study cohort and followed passively using secondary electronic data sources as in an observational study. A random sub-sample (50%) is selected from this cohort to be offered CC services, thus, encouraging such patients to engage in the CC program. The remaining 50% from the study cohort (not randomly selected to be offered the CC program) are thus the "usual care" comparison group and are never contacted by research staff, thereby eliminating the chance of activating behavior changes in the control arm due to study outreach, recruitment or assessments.

All those randomly selected to be offered the intervention—CC services—are included in the analysis, regardless of whether they are reached and choose to participate in the MI-CARE intervention or not.

This approach allows more flexibility in how and when a patient is engaged in the CC intervention, thereby potentially better representing patient-driven real-world care. The trial is patterned after CC as it would be offered in real-world practice. Consequently, a modified oral consent will be obtained at the time CC is offered to patients in the intervention arm. Some patients with documented OUD diagnoses may not recognize they have an OUD, or the diagnosis may have been placed in error, so our outreach initially focuses on depressive symptoms ("stress and low mood") and things that impact stress and low mood like pain, sleep, medications, or substance use.

To avoid the bias of getting only those willing to engage in research - outreach and the offer of CC are designed to mimic routine clinical care (while still fully informing CC arm patients they are participating in research), and outcomes data are collected entirely from electronic sources (e.g., EHR, claims data, prescription monitoring programs, and other clinical data bases) for all eligible and randomized patients.

3 OBJECTIVES AND OUTCOMES

3.1 OBJECTIVES

The MI-CARE trial evaluates the effectiveness of an offer of 12 months of CC to primary care patients with evidence of depression and OUD compared to usual primary care. The MI-CARE intervention is designed to support "whole health" by engaging patients in medication treatment for OUD and depression, reducing depressive symptoms, and addressing common comorbid conditions that complicate OUD and depression (e.g., anxiety, pain, sleep, and other mental health and substance use disorders).

3.2 MAIN OUTCOMES

Outcomes are evaluated in the total population-based cohort of primary care patients randomized for the trial based on documented depression symptoms and evidence of an OUD in the prior year in electronic data sources. All outcome measures are obtained from secondary health services information that can be obtained for the entire study cohort (e.g., EHR, claims, health information exchanges and State prescription monitoring programs). No primary data will be directly collected from participants for outcomes because 50% of patients are never contacted by the study.

3.2.1 PRIMARY TRIAL OUTCOME

AIM 1. Days of OUD medication treatment. A continuous measure of days of OUD treatment with buprenorphine in the 365 days after randomization.

Rationale: We use days of OUD treatment with buprenorphine as our main outcome to reflect both buprenorphine initiation and/or retention. Days of OUD medication treatment was recently selected and prioritized as the most important core outcome measure in a Core Outcome Set by a NIDA Clinical Trials Network Delphi process. We also include several secondary measures of OUD treatment. Although a consensus is emerging that days of OUD treatment is the optimal measure for OUD

treatment, these secondary measures will provide a fuller picture of treatment in our sample: days of any medication treatment for OUD, sustained buprenorphine treatment for OUD for 90 days, 30 buprenorphine treatment for OUD with 80% of days covered, and any OUD or other addiction treatment. We restrict to buprenorphine because it is the first line office-based treatment and therefore represents most office-based OUD treatment, and because injectable naltrexone and methadone treatment for OUD cannot be obtained consistently through the Health Information Exchange in Indiana.

We will obtain buprenorphine treatment data for the primary outcome using pharmacy and insurance claims data on dispensed buprenorphine in KPWA, and EHR buprenorphine orders and claims data available in IUH. These data sources have been used in prior studies, including the recent PROUD trial conducted by the NIDA CTN. At the same time, we recognize that patients in the MI-CARE usual care arm may be more likely to receive OUD treatment outside the healthcare system (in the absence of NCM support), which would be missed by these data systems, and could bias study outcomes. We therefore are making every effort to obtain more complete data from state prescription monitoring programs (PMPs) which are now available for research in both Indiana and Washington. State PMPs are the preferred data source because state level data provide the most unbiased source of our main outcome. However, because the process for PMP linkage is new to both sites, and state IRB applications require months, we cannot confirm feasibility at this time. If we obtain PMP data for the trial sample from both states, we will use it to measure the main outcome for the MI-CARE trial, as well as secondary outcomes based on buprenorphine or other opioids. If funding and time allow, we would also compare the main outcome measured with PMP data and the main outcome measured with EHR data, for a secondary paper to inform future pragmatic trials.

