13 DATA HANDLING AND RECORD KEEPING

13.1 QUALITY AND ACQUISITION OF AUTOMATED DATA FOR ANALYSES

All data needed to implement the SAP for the trial will be collected from automated data sources both internal (e.g., EHRs) and external to the health systems (e.g., insurance claims or HIE, PMP). The study will conduct routine checks of data collected from electronic health systems and look for data anomalies (e.g., missing, out of range). These data sources will be:

	KPWA	IUH	SOURCE
Electronic health system records	\boxtimes	\boxtimes	EHR, data warehouses
External hospital and emergency dept use		\boxtimes	Indiana health information exchange
External hospital and emergency dept use	\boxtimes		Insurance claims
Buprenorphine and other opioid data			State Prescription Monitoring Programs, claims, EHR records
Buprenorphine and other opioid data			Pharmacy data, Insurance claims
Buprenorphine and other opioid data			Indiana health information exchange
Death records	\boxtimes	\boxtimes	State departments of health

Research staff at KPWA and IUH may need to conduct targeted manual chart reviews to understand data for specific patients with data anomalies (e.g., duplicate orders, two hospital stays on the same day, hospital discharge date precedes the admit date). In addition, focused structured chart abstraction will be conducted for all study enrollees to validate quality (and potentially supplement) automated EHR data regarding patient clinical and demographic characteristics and receipt of study-relevant clinical services at the time of study enrollment. Such information may serve as important predictors of study outcomes. While conducting these chart reviews, our abstractors will also review the electronic health record for any known patient death data (e.g., date of death, cause of death, etc.). Although we hope to receive the most complete validated death data from Washington state via our pre-existing KPWA institutional data sharing agreement, we may not be given approval to send the state data to the Indiana honest broker site where we'll be conducting our trial analyses. We will transfer the most complete death data we are able to gather from the EHR chart abstractions, pending availability of the state death data and approval to transfer it to Indiana.

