13.3 DATA COLLECTION AND MANAGEMENT RESPONSIBILITIES

Data collection will be the responsibility of study staff at each enrollment site and under the supervision of the site investigators. The site principal investigators will be responsible for ensuring the accuracy, completeness, and timeliness of the data reported.

Each enrollment site is responsible for obtaining and quality checking data received from State sources (e.g., PMP, death and HIE records). Study programmers will extract, quality check and transform health system records to the study's data dictionary specifications using coded SAS® programs.

To obtain state PMP data, after each site obtains state IRB approval, bidirectional data use agreements will be arranged to allow linkage and transfer of data sets, or analysis on an honest broker site approved by the state. IUH will securely transfer limited data sets (not including Indiana PMP data) to KPWA, which serves as the data coordinating center, under the terms of a data use agreement. KPWA will then create and securely transfer a limited data set with both KPWA (including Washington PMP data) and IUH data needed for the final trial analysis to the IUH honest broker site to merge with the IUH PMP data (which cannot leave the state of Indiana). Only specific data team members (i.e. biostatisticians, data scientists, programmers) will have access to the full trial dataset on the Indiana honest broker site, per the terms of a separate data use agreement per personnel accessing the enhanced research environment.

Analytic data sets will be created without any values being overwritten by project staff. Values may be recoded into new variables for analyses, to preserve the original record. Final analytic datasets will be saved electronically, clearly labeled and stored in a secure project folder on the KPWHRI server accessible only to project staff.

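### Does the protocol leave the primary outcome without a defined data source if only one state supplies prescription monitoring data?

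*Protocol*

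**What the plan says.** Protocol section 3.2.1 sets the source of the primary outcome in three steps.

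- It names a source for each site without condition: pharmacy and insurance claims for dispensed buprenorphine at Kaiser Permanente Washington (KPWA), and "EHR buprenorphine orders and claims data available in IUH" (Indiana University Health).
- It warns that "patients in the MI-CARE usual care arm may be more likely to receive OUD treatment outside the healthcare system", that such treatment would be missed, and that this could bias the outcomes. It therefore ranks the sources: "State PMPs are the preferred data source because state level data provide the most unbiased source of our main outcome".
- It says feasibility cannot yet be confirmed and gives the rule: "If we obtain PMP data for the trial sample from both states, we will use it to measure the main outcome".

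A comparison of the two sources is optional: "If funding and time allow, we would also compare the main outcome measured with PMP data and the main outcome measured with EHR data".

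Section 8.4 (handling of missing data) lists health record, dispensing and claims, and PMP data together for Aim 1. It does not repeat the both-states condition, but adds that PMP data are not assured. Section 13.3 gives the route: "To obtain state PMP data, after each site obtains state IRB approval, bidirectional data use agreements will be arranged". Indiana's PMP data must stay in Indiana, so Washington's would be sent there for the final analysis.

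**The concern.** PMP data are committed to only for the case where both states deliver, and separate state approvals could leave just one. Section 13.1 already foresees a similar obstacle for Washington death records: "we may not be given approval to send the state data to the Indiana honest broker site". The most natural reading of section 3.2.1 would then leave the source the authors call least biased unused at the site that has it. Under-counting outside treatment in usual care would favor the intervention, the direction of the trial's hypothesis. Because section 8.4 lists all sources without the condition, a reader could also suspect that the source might be chosen late. The stakes would be some bias in the primary estimate, an inflated type I error and a discretionary choice on the main endpoint.

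**Working it through.** **The protocol's own figure.** Inputs from section 8.1.1: 760 analyzed patients (380 per arm), SD 98.3, two-sided alpha 0.05, power 80%.

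- SE = 98.3 × √(2/380) = 7.13 days. Detectable difference = 7.13 × (1.960 + 0.842) = 19.98, against the stated 20.
- With R² = 0.4: SE = 98.3 × √0.6 × √(2/380) = 5.52. Detectable difference = 15.48, against the stated 15.5.

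**The text, case by case.**

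| PMP data obtained from | Source under section 3.2.1 |
|---|---|
| both states | PMP, stated |
| neither state | health-system records, stated |
| one state | condition not met, so health-system records at both sites, by inference |

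Section 8.4 names no rule that competes with this. It lists possible sources and says one of them is uncertain.

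**Bias if health-system records are used throughout.** The documents give no capture rates, so these are assumptions: 46.7 days (section 8.1.1) are the true usual-care days; health-system records capture a share of days g larger among engaged patients than in usual care; there is no gap among the non-engaged; engagement is e. Then b = 46.7 × g × e, and two-sided type I error = 1 − Φ(1.96 − b/SE) + Φ(−1.96 − b/SE).

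| g | e | b (days) | b / 20 | Type I error, R² = 0 | Type I error, R² = 0.4 |
|---|---|---|---|---|---|
| 0.10 | 0.35 | 1.63 | 8% | 5.6% | 6.0% |
| 0.20 | 0.50 | 4.67 | 23% | 10.0% | 13.5% |

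**What PMP data at one site would gain.** Let s be the linked site's share of the bias (assumed 0.25 to 0.75) and r the part that PMP data remove there (assumed 0.8 to 1.0). The residual is b × (1 − s × r), a factor of 0.80 (1 − 0.25 × 0.8) down to 0.25 (1 − 0.75 × 1.0).

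- 1.63 days falls to between 1.31 and 0.41; type I error at R² = 0 goes from 5.6% to 5.4–5.0%.
- 4.67 days falls to between 3.74 and 1.17; type I error at R² = 0 goes from 10.0% to 8.2–5.3%.
- If the under-capture sits almost wholly at the unlinked site, s is near 0 and nothing is gained.

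**A second illustration, with a true effect.** Take true means of 46.7 and 66.7 days, and assume capture of 90% in usual care and 95% in the intervention arm. Health-system records give 66.7 × 0.95 − 46.7 × 0.90 = 21.3 days. If half the patients have complete PMP data, the pooled value is (21.3 + 20)/2 = 20.7. With 80% and 95% capture the values are 26.0 and 23.0. The choice of source moves the estimate by about 1 to 3 days. The mixed version averages two different quantities, 20 days at one site and 21.3 or 26.0 at the other.

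**How firm the direction is.** Section 6.4.1 has the nurse care manager help patients obtain treatment from outside providers as well as from primary care. Suppose this adds x outside days per engaged patient that health-system records miss. The net bias is e × (46.7 × g − x), which is zero at x = 4.67 days for g = 0.10 and at x = 9.34 days for g = 0.20. A few extra outside days per engaged patient would cancel the assumed bias.

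**The case for a change.** The strongest case for a change is that section 3.2.1 does not defer this matter. It sends covariate selection and multiple depression scores to the statistical analysis plan, but states a rule for the outcome source, and that rule is silent on one plausible outcome. Randomization is stratified by site and the model adjusts for health system, so using PMP data for both arms at a linked site would keep the randomized comparison. The defaults already differ between sites (dispensing against orders), so uniformity is not fully available anyway. The change would cost little.

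Part of this stands. The one-state case is not written down, section 8.4 is looser than section 3.2.1, and mixing sources would not by itself confound the comparison of arms.

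It does not show an error. Within-site randomization protects either choice, so it does not favor mixing. Both defaults are at least health-system measures; mixing would add a statewide measure at one site only, for the outcome and for its baseline covariate. Avoiding that is a fair reason for the both-states condition. A one-state result is possible but not singled out anywhere: the death-record caveat concerns a different file, and section 13.3 sets out how Washington PMP data would reach Indiana. Room for a convenient late choice is small, because availability depends largely on state approvals and section 10.3 keeps the study team from seeing outcomes by arm during the trial. The optional comparison of sources is meant for a secondary paper; it does not limit the sensitivity analyses that a statistical analysis plan may contain.

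**Conclusion.** No change is needed. The protocol gives each site a source and replaces it if both states supply PMP data, so the fallback can be inferred. Spelling out that fallback is routine for the statistical analysis plan, which was not among the documents at hand. The joint list in section 8.4 is loose wording that an analyst would read together with section 3.2.1.

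Whether to mix sources across sites is a design choice with a cost on each side. The case that the present rule does worse needs three things the documents do not supply: a probability that exactly one linkage succeeds, a capture gap between arms, and a settled direction for the bias. With an assumed gap of 10 to 20 points and 35 to 50% engagement, the bias is 1.6 to 4.7 days. What one-site PMP data would recover ranges from almost nothing to three quarters of it.
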